5.6. Prior and Concomitant Medications/Procedures

Medications will be coded using the World Health Organization Drug Dictionary (March 2019 or later); and procedures will be classified by the MedDRA coding system (version 23.0 or later).

Medications will be classified as prior and/or concomitant. Prior medications are those medications with start date prior to the first dose of study drug, regardless of medication end date. If the medication end date is before the date of first dose of study drug, the medication will be summarized as prior medication regardless of whether the start date is missing or not. Concomitant medications are medications, other than the study drug, that have a start date on or after the date of first dose of study drug, as well as medications that started before the date of first dose of study drug and are ongoing after the first dose of study drug (or have an imputed end date after the first dose of study drug) and through the first dose in the OLE period for patients who entered OLE, or the earlier of (84 days after the last dose of study drug, early study discontinuation) for patients who discontinued DB treatment for the outputs during the DB period. Unique patients who reported medications will be summarized by Anatomical Therapeutic Chemical (ATC) level 3 class (or level 2 if not available) and PT. Summaries will be provided for prior and concomitant medications separately using Safety Analysis Set.

Similarly, procedures will be classified as prior and/or concomitant. Unique patients who report procedures during the DB period will be summarized by MedDRA system organ class (SOC), high level term (HLT) and preferred term (PT).

When there are partial or missing dates, imputed dates will be used to determine 1) if a medication/procedure is prior or concomitant, and 2) duration of exposure to select medications/procedures, as needed. Imputed dates will not be presented in the listings. The imputation rule is documented in Appendix 9.7.

For patients who are not on baseline tafamidis, tafamidis drop-in after the date of the first dose of study drug will be summarized, including but not limited to: number and percent of patients with drop-in as well as descriptive statistics for the time from the first dose of study drug to the tafamidis drop-in.

For patients who are taking tafamidis at baseline, tafamidis disease progression signs and symptoms prior to the baseline will be summarized.

CCI

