5.7.5. Additional Analyses

An alternative estimand is to assess vutrisiran compared to placebo in the vutrisiran monotherapy subgroup without concomitant use of tafamidis.

- For the composite outcome endpoint, events collected beyond 9 months of tafamidis drop-in will be censored. The same LWYY model as for the primary analysis will be applied.
- For 6-MWT and KCCQ-OS, assessments after tafamidis drop-in will be excluded from the MMRM analysis. Missing data due to death and unable to walk due to progression of ATTR amyloidosis (for 6-MWT only) will not be imputed.

For continuous efficacy endpoints, descriptive statistics will be provided for actual value and change from baseline by visit; descriptive statistics for percentage change from baseline by visit may also be provided, as appropriate.

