 - if the start date is complete, impute the end date as the day after the start date.
 - if the start date has missing day only, impute as the last day of the same month of the start date.
 - if the start date has missing month and day, impute as the last day of the month and year as the first dose date.

Start date imputation:

- if only day is missing
 - if the start date and end date have the same month, impute the missing day as the day before the end date.
 - if the start date and end date have different months, impute as the last day of the month.
- if both day and month are missing, impute as the date before the end date.
- if complete missing, impute the missing date as the date before the end date.

Medications:

- For medications with missing month/day for start or end dates:
 - For start dates, missing month will be imputed as January and missing day will be imputed as the first day of the month.

- For end dates, missing month will be imputed as December and missing day will be imputed as the last day of the month.
- For medications with completely missing start or end dates:
 - Missing start date will be imputed as one day prior to the first dose of study drug. If the imputed start date is after the collected end date, the end date will be used as the imputed start date.
 - Missing end date will be imputed as the earliest date of study discontinuation date, cutoff date, or death date.

Adverse events and Procedures:

Partial or missing AE or procedure end dates will not be imputed. For AE or procedure start date:

- If year is missing, set to the first dose date. If this leads to a date after the end date (when end date is available with partial or complete information), set to the end date.
- If year is not missing, but both day and month are missing:
 - If year of the start date is equal to the year of the first dose date, set to the first dose date.
 - If year of the start date is not equal to the year of the first dose date, impute the missing day and month of the start date as January 1st.
 - If the imputed date leads to a date after the end date, impute the missing day and month of the start date using the day and month of the end date.
- If only day of the start date is missing:
 - If the year of the start date is equal to the year of the first dose date, and the month of the start date is equal to the month of the first dose date, impute the missing day of start date using the day of the first dose date.

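### SAP 9.7 dates a partial or missing tafamidis start as early as possible with no first-dose floor, so a drop-in can be dated too early or lost from the drop-in summary

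*SAP*

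**What the plan says.** The medication part of SAP 9.7 covers every drug with the same rule. For a partly known start, "For start dates, missing month will be imputed as January and missing day will be imputed as the first day of the month". For a start with nothing recorded, "Missing start date will be imputed as one day prior to the first dose of study drug", unless a recorded end date is earlier. There is no floor at first dose and no exception for tafamidis.

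The rule for adverse events and procedures, in the same appendix, does have a floor. With month and day unknown, "If year of the start date is equal to the year of the first dose date, set to the first dose date", and a start in the month of first dose with only the day unknown is handled in the same way.

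SAP 5.6 puts the imputed dates to use: "When there are partial or missing dates, imputed dates will be used to determine 1) if a medication/procedure is prior or concomitant", and also for duration of exposure to selected medications. It defines the class by the start: "Prior medications are those medications with start date prior to the first dose of study drug, regardless of medication end date". It then says: "For patients who are not on baseline tafamidis, tafamidis drop-in after the date of the first dose of study drug will be summarized". That summary includes the time from first dose to drop-in.

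SAP 5.7.5 describes an alternative estimand for the monotherapy subgroup. For the composite, "events collected beyond 9 months of tafamidis drop-in will be censored". For 6-MWT and KCCQ-OS, values obtained after drop-in are left out of the MMRM.

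**The concern.** For most medications an early imputed start does no harm. Tafamidis differs because its start is a named intercurrent event. SAP Table 6 says that a high or unequal drop-in rate would confound the treatment effect, and refers that question to SAP 5.7.5. The drop-in count and the drop-in date are therefore the evidence on which a reader would judge the risk.

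For a patient enrolled off tafamidis, the trial knows more than the rule uses. The patient was not on the drug at baseline. Protocol 5.4.1 also requires monitoring of tafamidis use throughout and a Pre-tafamidis Drop-in Visit before tafamidis is started. An imputed start before Day 1 contradicts the first fact, and one before that visit contradicts the second. The error has one direction: for a true start after first dose, every branch gives a date on or before the truth.

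**Working it through.** The plan gives no figure to reproduce. The check applies the rule to dates.

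**Inputs.** The imputation rule is from SAP 9.7, the prior and drop-in definitions from SAP 5.6, and the 9-month cut from SAP 5.7.5 (274 days in the worked dates). Three assumptions are not in the documents:
- A year-only start has a true date uniform over its year.
- First dose is uniform from January 2020 to August 2021. Only the August 2021 close of enrolment is documented, in the Amendment 3 summary.
- Drop-in is uniform over study days 1 to 1085.

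**Step 1. Days early = true start − imputed start.**
- Day missing: 0 to 30 days, mean about 15.
- Month missing: 0 to 365 days, mean about 182 (12 months / 2 = 6 months).
- All missing: the whole time since first dose, plus 1 day.

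**Step 2. Worked dates, first dose 15 March 2021.**

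| True start | Missing | Imputed start | Days early | Against first dose | 9-month cut |
|---|---|---|---|---|---|
| 20 Nov 2021 | month, day | 1 Jan 2021 | 323 | before | 2 Oct 2021 |
| 28 Mar 2021 | day | 1 Mar 2021 | 27 | before | 30 Nov 2021 |
| 20 Nov 2022 | month, day | 1 Jan 2022 | 323 | after | 2 Oct 2022 |
| 20 Nov 2022 | all | 14 Mar 2021 | 616 | before | 13 Dec 2021 |

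Rows 1, 2 and 4 no longer meet the SAP 5.6 condition of a start after first dose. Row 3 still counts, but its cut falls 49 days (1.6 months) before tafamidis began. Under the adverse-event rule, the year-only record in row 1 would be dated 15 March 2021.

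**Step 3. How often a drop-in is dated before Day 1.** Simulation, 100,000 drop-ins per case:

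| Drop-in on study days | Month missing | Day missing | All missing |
|---|---|---|---|
| 1 to 1085 | 19% | 1.3% | 100% |
| 1 to 365 | 56% | 3.8% | 100% |
| 365 to 1085 | 0% | 0% | 100% |

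**Step 4. Composite cut for a year-only start.** 1 January + 9 months = 1 October. The share with a true start on or after 1 October is (31 + 30 + 31)/365 = 92/365 = 25.2%. The simulation, with 274 days, gives 24.7% to 24.8%. Because the cut moves with the start, the follow-up lost equals the shift, about 6 months on average if the patient would otherwise have been followed that long. The part of it before tafamidis began is at most 92 days. The rest is time after the start that the 9-month allowance was meant to keep.

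**Step 5. 6-MWT and KCCQ-OS.** The double-blind visits in SAP Table 4 are at Weeks 24, 48, 72, 108 and 132, so 24 to 36 weeks apart. A mean shift of 182/7 = 26 weeks wrongly removes roughly one visit per affected patient.

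**The case against.** The case against has real force.

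- **No main result depends on this date.** Drop-in is handled by treatment policy in the primary analyses of the composite (SAP Table 6), 6-MWT and KCCQ-OS (Table 8), all-cause mortality (Table 9) and NYHA class (5.7.2.3.1). A reader might infer that the primary p-values or the multiplicity procedure are at risk. They are not.
- **Baseline group.** A reader might infer that an imputed start before Day 1 moves a monotherapy patient into the background-tafamidis group. Nothing in the documents says that baseline use is derived from imputed dates. SAP 4.4 takes the stratum as recorded in the clinical database.
- **Medication tables.** A reader might infer that a misdated course leaves the concomitant-medication table. It does not: under SAP 5.6, a course that starts before first dose and is still ongoing is both prior and concomitant. Only the drop-in summary can lose it.
- **The link to SAP 5.7.5 is inferred.** SAP 5.6 names two uses of imputed dates, and censoring is not one of them. No other visible rule dates drop-in, but text near the drop-in paragraph is redacted, so a specific rule cannot be ruled out.
- **Few cases.** Exclusion criterion 7 keeps out patients expected to start tafamidis in the first 12 months, which makes starts in the year of first dose less likely. The drop-in visit and data cleaning should make partial dates rare. The only drop-in rate given is below 1% as of May 2021, an early figure.
- **Early dating can be defended** for an estimand without tafamidis, since it keeps on-tafamidis data out.

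These points limit the size and reach of the problem. They do not make the rule right. The last one does not justify a date before Day 1 or before a recorded drop-in visit, and exclusion criterion 7 does not affect the shift of later year-only starts to 1 January.

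**Conclusion.** The concern holds as a defect in a stated rule with limited reach. On the text, a true drop-in is always dated before Day 1 if its start date is fully missing. The same can happen if the date is partial and falls in the year or month of first dose. Such a patient drops out of the SAP 5.6 drop-in summary if that summary uses the imputed dates, as the section implies. A later year-only start is dated up to 12 months early, about 6 on average.

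If the same dates feed SAP 5.7.5, valid pre-tafamidis 6-MWT and KCCQ-OS values are excluded. Composite follow-up then ends before tafamidis began in about 25% of year-only cases. Both the 6-month mean and the 25% rest on uniform true dates.

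The number of partial tafamidis dates is not given and is probably small, so the effect on any output is unknown. It is still worth correcting: SAP 5.7.5 is the plan's own check on a confounder that it names, and a few misdated cases weigh more when drop-ins are few.

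**What to change.** Add a tafamidis rule to SAP 9.7. It would apply in patients not on tafamidis at baseline, to courses ongoing at first dose or ending after it. Impute a partial or missing start as the latest of:

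1. the first day compatible with the recorded part;
2. the day after first dose;
3. the day after the Pre-tafamidis Drop-in Visit, if one was held.

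Keep the result within the recorded year or month, and no later than any recorded end date. Leave earlier courses of former users unchanged, because inclusion criterion 4a counts patients off tafamidis for at least 30 days before Screening as naïve. State in SAP 5.6 and 5.7.5 that this date defines drop-in.

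The rule need not cover the other therapies in Table 6, since the visible text of SAP 5.7.5 uses only the tafamidis date. Nor should it rely on dated negative tafamidis checks: the protocol's Table 1 shows the check only as continuous.

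The cost is a short SAP paragraph and a small programming change. The dose, visit and medication dates are already collected.

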5.11.1. Adverse Events

AEs will be classified by the MedDRA coding system (version 23.0 or later) and displayed in tables and data listings using SOC and PT, unless otherwise specified.

Analyses of AEs will be performed for those events that are considered treatment-emergent, defined as any AE occurring or worsening on or after the first dose of study drug and through the first dose in the OLE period for patients who entered OLE, or the earlier of (84 days after the last dose of study drug, early study discontinuation) for patients who discontinued DB treatment, or

any study drug-related AE. Events with a fully or partially missing onset date will be imputed according to the imputation rule defined in Appendix 9.7 before determining treatment-emergent or not.

Unless otherwise specified, AEs will be summarized by the numbers and percentages of patients reporting a given AE, as well as number of AEs and event rates per 100 patient-years.

An overall table of TEAEs will include:

- any AE
- any AE related to study drug
- any serious adverse event (SAE)
- any SAE related to study drug
- any severe AE
- any severe AE related to study drug
- any AE leading to treatment discontinuation
- any drug-related AE leading to treatment discontinuation
- any AE leading to study drug interruption
- any treatment-related AE leading to study drug interruption
- any AE leading to study discontinuation
- any drug-related AE leading to study discontinuation
- any AE leading to death including those not treatment emergent but deaths occurred after the end of study visit are not included.

Tabulations by SOC and PT will be produced for the following:

- AEs
- Treatment-related AEs
- Severe AEs
- SAEs
- AEs leading to treatment discontinuation
- AEs leading to treatment interruption
- AE leading to study discontinuation
- AEs over time

Tabulations by SOC and PT will be produced for AEs with a higher frequency ($\geq 5\%$ or $\geq 10\%$) in either treatment group.

Tabulations by PT will be produced for the following:

- AEs

- Treatment-related AEs
- SAEs

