6. OTHER STATISTICAL ANALYSES

6.1. During Vutrisiran Treatment Period

The long-term safety of vutrisiran will be characterized by the analysis of All Vutrisiran treated Set for the vutrisiran treatment period (Section 4.1). The analysis will include all data on or after the first dose of vutrisiran during either the DB or OLE period:

- For patients who receive vutrisiran in the DB period, data from the DB and OLE periods will be integrated.
- For patients who receive placebo in the DB period and receive at least one dose of vutrisiran in the OLE period, only data after the first dose of vutrisiran in the OLE will be included.

Where applicable, baseline will be defined as described in Section 4.3. Summaries will be presented by placebo/vutrisiran, vutrisiran/vutrisiran, and total for the All Vutrisiran treated Set.

Duration of drug exposure will be defined as last vutrisiran dose date – first vutrisiran dose date + 1, with last vutrisiran date defined as the earliest of the following dates:

- Last vutrisiran dose date + treatment-specific window (83 days if last vutrisiran dose received is 25 mg q3M; CCI [REDACTED])
- Analysis cutoff date
- End of study date

AE and ISR summaries described in Section 5.11.1 will be provided for vutrisiran-emergent adverse events, defined as treatment-emergent adverse events occurring on or after the first dose of vutrisiran treatment through a treatment-specific window following the last dose of vutrisiran (83 days if last vutrisiran dose received is 25 mg q3M; CCI [REDACTED])

[REDACTED] Potentially clinically significant postbaseline abnormalities and shift from baseline to the worst postbaseline status for laboratory, vital signs, and ECG parameters, ADA, concomitant medications, and overall study drug exposure, during the vutrisiran treatment period will be summarized.

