 - Otherwise, impute the missing day of the start date as 1.
 - If the above leads to a date after the end date, impute the missing day of the start date using the day of the end date.

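### SAP 9.7 has no date anchor at the first open-label dose, so partly dated adverse events around OLE entry in former placebo patients are counted as double-blind placebo events

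*SAP*

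**What the plan says.** SAP Section 9.7 gives one rule for incomplete onset dates of adverse events. It has three branches, all tied to the first dose date:

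- Year missing: "If year is missing, set to the first dose date".
- Day and month missing: the first dose date if the year matches; otherwise, under "If year of the start date is not equal to the year of the first dose date", 1 January of the reported year.
- Day only missing: the day of the first dose if year and month match; "Otherwise, impute the missing day of the start date as 1".

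A check against the end date follows each branch. It acts only when the imputed start falls after the end date, so it can only move a start earlier.

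SAP Section 5.11.1 makes this rule decide the classification: "Events with a fully or partially missing onset date will be imputed according to the imputation rule defined in Appendix 9.7", and this is done before treatment emergence is determined. For patients who enter the OLE, the double-blind window covers "any AE occurring or worsening on or after the first dose of study drug and through the first dose in the OLE period". Section 5.11 uses the same window for the safety summaries.

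SAP Section 6.1 defines vutrisiran-emergent events as those "occurring on or after the first dose of vutrisiran treatment". For former placebo patients it admits only data after their first OLE dose. It gives no date rule of its own.

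**The concern.** At the first double-blind dose the rule resolves doubt towards exposure: a partial date in that month or year is moved onto the dose date, and the event becomes treatment-emergent. A placebo patient has a second first exposure, at OLE Day 1, and there the rule resolves doubt the other way. It moves the onset to the start of the month or year, before vutrisiran was given.

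Elsewhere the SAP treats OLE entry as a new start for these patients. Section 4.3 resets their baseline, and the note to Table 1 in Section 4.1 redefines their tafamidis subgroup. Section 5.11.1 takes missing severity as severe and missing relatedness as related. The onset-date rule alone lacks the matching step.

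At stake is which drug an event is attributed to. Section 6.1 is the planned description of long-term vutrisiran safety, and Protocol Section 1.7 names injection-site reactions and liver-test abnormalities as the important potential risks. The issue reaches the Primary Analysis too: under SAP Section 4.2 its cutoff falls at about the time the last patient enters the OLE, so earlier patients already have OLE data.

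**Working it through.** The plan states no figure here, so the check follows the rule through and then asks how far it reaches.

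**1. Which branch applies at OLE entry.** SAP Section 2.1 places OLE Day 1 at 144 or 156 weeks (±7 days). The earliest is 144 × 7 − 7 = 1001 days after enrollment. A calendar year has at most 366 days, so OLE Day 1 never falls in the first-dose year. The 1 January and 1st-of-month branches therefore always apply.

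**2. Worked example.** First dose 15 September 2020; OLE Day 1 is 156 weeks (1092 days) later, 12 September 2023.

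| True onset | Recorded as | Imputed onset |
|---|---|---|
| 15 Sep 2023 | Sep 2023 | 1 Sep 2023 |
| Oct 2023 | 2023 | 1 Jan 2023 |
| 15 Sep 2023 | year missing | 15 Sep 2020 |

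All three precede the first vutrisiran dose. In general the 1st of the entry month and 1 January of the entry year cannot be later than OLE Day 1. They equal it only if that dose was given on the 1st, or on 1 January.

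**3. Which column.** The imputed date lies inside the double-blind window. SAP Section 3 regroups a placebo patient only for vutrisiran received during the DB period, so OLE dosing does not trigger it. The event is tabulated under placebo.

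**4. Section 6.1.** If the first dose date means the first study-drug dose, as the Day 1 definition in SAP Section 4 suggests, an onset imputed before OLE Day 1 is excluded from the placebo/vutrisiran column. If it means the first vutrisiran dose for that analysis, the event is kept. The SAP does not say which.

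**5. Reach in time.** The rule was applied to 200,000 simulated patients. Assumptions: first dose uniform from 22 August 2019 (original protocol date) to 31 August 2021 (enrollment ended that month, Protocol Section 10.4.3); OLE Day 1 at 144 or 156 weeks with equal chance, ±7 days; true onset uniform after OLE Day 1.

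- True post-OLE onsets in the entry month with day missing, or in the entry year with day and month missing: 100% imputed on or before OLE Day 1.
- Mean time left after OLE Day 1: 14.7 days in the month, 182 days in the year. The rest of the year holds 2.7 doses on average and at most 5 (84-day interval).
- Onsets in the first 84 days after OLE Day 1 that are moved back: 18% if the day is missing, 88% if day and month are missing, 100% if the year is missing.

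Hand check: 14.7/84 = 0.175. With entry spread evenly over the year, 1 − 84/(2 × 365) = 0.885.

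**6. Illustrative size.** The documents give no share of incomplete dates. Assuming 1% to 3% of former placebo patients' events in those 84 days, the share of such events moved is:

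- all day-missing: 0.01 × 0.176 to 0.03 × 0.176, about 0.2% to 0.5%;
- all year-only: 0.01 × 0.884 to 0.03 × 0.884, about 0.9% to 2.7%;
- all year-missing: 1% to 3%.

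**The case against.** Four arguments can be made against this point.

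- **Incomplete dates should be rare for the events that matter.** Protocol Section 6.5.6.2 requires an onset time and date for every event and an extra form for every injection-site reaction. Events of clinical interest and serious events are notified within 24 hours. The first OLE dose is given in clinic, with visits at OLE Weeks 6 and 12. This stands and keeps the count low. A reader might infer that every former placebo patient is affected; only those with an incompletely dated event that meets one of the three branches are.
- **The vutrisiran arm is treated alike.** Its OLE events also move back into the double-blind tables, under vutrisiran. A reader might infer a one-sided bias that hides harm in the randomized comparison. The documents do not support that: both columns gain events, and the net change may be small.
- **Section 6.1 may already use the first vutrisiran dose.** Baseline and data inclusion are re-anchored there for former placebo patients. A reader might take the loss from 6.1 as certain; it depends on a meaning the SAP leaves open. The wrong label in the double-blind tables does not depend on it.
- **Some of these events really are placebo-period events.** With OLE entry on 20 May, 19 of the month's 31 days come before it. True, but the rule never allows the other possibility.

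Safety is also descriptive throughout (SAP Section 5.11), so no test rests on this rule.

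**Conclusion.** The gap is real and follows from the text. A placebo patient's event known only to the OLE entry month or year, or with no year, is counted as a double-blind placebo event even if it followed the first vutrisiran dose. Whether it is also lost from the placebo/vutrisiran column in Section 6.1 depends on which dose the anchor means there.

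The day-missing branch reaches only the rest of the entry month, in practice the first OLE dose. Later doses are reached only when the month or year is unknown.

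The likely count is small, and the range above rests on an assumed 1% to 3% of incomplete dates. The double-blind contrast may hardly move. The error that remains is a wrong drug label at the start of exposure for crossover patients. It merits correction because the repair is short and brings the date rule into line with the rest of the SAP.

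**What to change.** 1. In Section 9.7, state that for the vutrisiran-treatment-period analysis in Section 6.1 the first dose date means the first vutrisiran dose. For a DB-placebo patient who enters the OLE, an onset whose known parts match the month or year of the first OLE dose, or whose year is missing, is then set to that dose date unless the end date precedes it.
2. In Section 5.11.1, for DB-placebo patients only, state that an event so imputed to OLE Day 1 is vutrisiran-emergent and is not counted in the double-blind placebo column. This tie rule is needed because the double-blind window includes the OLE Day 1 date.
3. Leave the double-blind rule for the vutrisiran arm unchanged, so that true double-blind events are not taken out of the active column.
4. List the events reassigned in this way.

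The cost is a few lines of text and of derivation code. The downside is that some true placebo-period events will be counted as vutrisiran-emergent. This is worst for year-only dates with late entry: for entry on 20 November, 323 of 365 days (88%) come before it. The listing lets readers see the effect.
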